8.4.6 Death events

Any death that occurs within the observation period will be reported as an SAE, if not covered by the exemptions to the SAE definition as defined in Sections 8.4.7, 10.4.2, and 10.4.2.2, which do also apply for fatal cases. Date and cause of death will be recorded. If available, a copy of an autopsy report should be submitted if available upon request.

In case of a fatal event, the event term should not be "death" but the underlying event which led to death (death = outcome). If there is more than 1 AE in a fatal case, only for the AE leading to death the outcome "fatal" should be selected. If the cause of death is unknown and cannot be ascertained at the time of reporting, "unexplained death" should be documented as event term.

In addition to reporting as SAE, the death page of the eCRF needs to be completed.

Deaths clearly related to the progression of the disease will not be documented as AEs nor reported as SAEs if fatal progression/death is a trial endpoint. These deaths must be collected on the death page of the eCRF.

8.4.7 Disease-related events and/or outcomes not qualifying as AEs or SAEs

The progression of underlying disease (e.g., new metastases, death) during trial participation is not considered as an AE if fatal progression/death is a trial endpoint.

Because disease progression is common for patients with cancer, it will not be reported according to the standard process for expedited reporting of an SAE even though the event may meet the definition of a SAE. These events will be recorded on the corresponding page in the patient's eCRF as for SAEs.

NOTE: Symptoms resulting from the progression of the underlying malignant disease fatal cases clearly related to the progression will not be documented as AEs and reported as SAEs. However, specific symptoms at time of progression that are considered relevant but that may be caused by other reason, and fatal cases due to another reason than the disease progression may not be discarded. The findings will have to be documented as AEs and reported as SAEs if applicable.

8.4.8 Adverse events of special interest

An AE of special interest (AESI), serious or non-serious, is one of scientific and medical concern specific to the sponsor's product or program, for which ongoing monitoring and rapid communication by the investigator to the sponsor are appropriate. Such an event might warrant further investigation in order to characterize and understand it. Depending on the nature of the event, rapid communication by the trial sponsor to other parties (e.g., regulators) might also be warranted.

- Grade ≥3 infusion-related reaction related to BNT321
- Grade ≥3 AST or ALT or Grade ≥2 bilirubin elevation lasting ≥7 days, related to BNT321

NOTE: An irAE can occur shortly after the first dose or several months after the last dose of treatment. All AEs of unknown etiology associated with drug exposure should be

Page 81 of 127 Version: 2.0 Date: 22 JAN 2024

evaluated to determine possible immune etiology. If an irAE is suspected, efforts should be made to rule out neoplastic, infectious, metabolic, toxin or other etiologic causes prior to labeling an AE as an irAE.

AESIs including non-serious AESIs should be reported via the SAE Report Form according to the timelines and contact details given in Section 10.4.4 of this protocol. For non-serious AESIs, the seriousness criterion should not be reported/selected as these non-serious AESIs are to be reported according to the timelines of SAEs, but mostly do not have the seriousness of an SAE.

All AESIs will be followed until resolution, stabilization, the event is otherwise explained, or the patient is lost to follow-up (as defined in Section 7.3).

8.5 Pharmacokinetics

Planned time points for PK sampling to obtain plasma level BNT321 are provided in the SoA (Section 1.3, Table 3).

- The actual date and time (24-h clock time) of each sample should be recorded.
 Blood samples for PK analysis should be collected, handled, frozen and shipped as outlined in the Laboratory Manual.
- PK samples will be analyzed centrally by a specialty laboratory. Detailed instructions on collection of blood for BNT321 PK will be provided in the pharmacokinetic kit and Laboratory Manual.
- The sponsor may elect to adapt future collections of blood for PK levels based on previously generated PK data.

Leftover of samples collected for PK testing and of samples collected for immunogenicity testing can be used interchangeably if they were collected at the same timepoint and after the original purpose of the sample was fulfilled.

8.6 Genetics

No genetic analyses are planned for this trial.

8.7 Biomarker assessments

Sampling for biomarkers will be performed at the time points listed in Section 1.3.

Sample handling and storage – details on the collection, processing, shipment, and storage of samples will be provided in separate documents (e.g., sample handling sheets or laboratory manual). Samples may be stored for a maximum of 15 years (or according to local regulations) following the end of the trial at a facility selected by the sponsor to enable further analyses.

The following biomarker assessments will be done centrally by a specialty laboratory:

 PBMCs will be isolated from collected blood to measure ADCC activity over the course of time on trial. This sample will only be collected if logistically manageable.

Page 82 of 127 Version: 2.0 Date: 22 JAN 2024

- Serum will be isolated from collected blood to measure CDC activity over the course of time on trial.
- Serum will be isolated from collected blood to measure cytokine/chemokine levels for pharmacodynamic assessment.
- Plasma will be isolated from collected blood to track and measure circulating tumor DNA (ctDNA) over the course of treatment as a surrogate for tumor burden. In addition, specific mutations may be monitored over time to understand potential resistance mechanisms.
- FFPE tumor tissue from resection or biopsy will be obtained during screening. In
 the event of progression, a biopsy collection should be requested as optional. IHC
 expression of CA19-9 and expression of other biomarkers may be evaluated for
 exploratory analysis of correlations between expression levels and indicators of
 response. Tumor samples may also be examined using RNAseq as an exploratory
 analysis of gene signatures correlating with response and/or by whole exome
 sequencing (WES) to inform ctDNA analysis.

Biomarker analyses may be deferred or not performed, if during or at the end of the trial, it becomes clear that the analysis will not have sufficient scientific value for biomarker evaluation, or if there is not enough sample to allow adequate evaluation. If the trial is terminated early or shows poor clinical efficacy, completion of biomarker assessments in part or total is based on justification and intended utility of the data.

Medical history information – if any additional relevant information about the tumor, disease, or status of disease was collected during treatment prior to entry of the patient in the trial, these results may be taken into consideration during the biomarker analyses.

The results of biomarker investigations will be reported separately (e.g., in a biomarker evaluation report) instead of in the ICH E3 clinical trial report. All data generated using the biomarker samples, will be handled in accordance with applicable laws and regulations; this includes requirements applicable for data protection, for sample shipment outside Germany, and a potential withdrawal of consent.

8.8 Immunogenicity assessments

Immunogenicity samples will be collected from all patients on the combination therapy arm (will not be collected for the control arm). Planned time points for immunogenicity sampling (anti-BNT321 antibodies) are provided in the SoA (Section 1.3). An extra sample will be taken for re-testing of future analysis if required. Samples will also be collected at the final visit from patients who discontinued trial treatment or were withdrawn from the trial.

Samples and any data derived using the collected samples will be processed in compliance with the applicable regulations and GCP.

Blood samples for immunogenicity analysis must be collected, handled, frozen and shipped as outlined in the laboratory manual.

Page 83 of 127 Version: 2.0 Date: 22 JAN 2024

Immunogenicity samples will be analyzed by a specialty laboratory. All collection and storage tubes will be provided in the laboratory sampling kits.

Leftover of samples collected for PK testing and of samples collected for immunogenicity testing can be used interchangeably if they were collected at the same timepoint and after the original purpose of the sample was fulfilled.

8.8.1 Exploratory research analyses

Blood samples will only be used for exploratory analyses if the patients have provided separate informed consent for these analyses.

In selected patients, further exploratory research analyses can be conducted using residual biological samples from subsets of patients in order to further characterize the mechanism of action of the antibody treatment, e.g., additional characterization of patient tumor, PBMCs, serum, and plasma.

Exploratory research analyses will be planned, conducted, and reported in accordance with the sponsor's standard operating procedures (SOP).

Biosamples for research analyses will be retained for use for up to 15 years (or shorter if required by local regulations) after the end of the trial. The tube with the biosample will be labeled with a number (optionally also with a bar code) and will not include information that could be used to identify the patient. Results of the analyses will be linked to the clinical information collected during the trial using this specific number. The analysis will only be carried out on the basis of the label data and biosamples. Research biosamples and all data generated using the biosamples, will be handled in accordance with applicable laws and regulations; this includes requirements applicable for data protection and a potential withdrawal of consent.

The patient may withdraw consent for future use of research samples at any time. To initiate the sample destruction process, the investigator must notify the sponsor of withdrawal of consent for the research samples and to request sample destruction. The sponsor will then initiate the process for sample destruction. If requested, the investigator will receive written confirmation from the sponsor that the samples have been destroyed. If the patient withdraws consent for research samples, the sponsor may retain and continue to use any data from samples already analyzed before such a withdrawal of consent. Samples will be destroyed after they are no longer needed for the clinical trial.

8.9 Other assessments

No other assessments are planned.

8.10 Blood collection

According to trial SoAs the total blood volume drawn over any 2-week cycle in any group will be less than 115 mL. Additional blood samples may be taken, e.g., for safety assessments of AEs or SAEs.

Page 84 of 127 Version: 2.0 Date: 22 JAN 2024

As long as the absolute volume of blood drawn does not change per patient overall, the volume of individual blood draws may be adapted if required, e.g., due to unforeseen shortage of specific tubes. Leftover or back up clinical sample aliquots of a patient, which have the exact same collection times, intended to a particular assessment can be used for another assay than that stated on the label if both assessments are described in the SoA and, the patient has consented to all. This is only possible if a primary sample has been used first for its original purpose and it is confirmed that no re-testing is required. Samples can only be used interchangeably if the sample characteristics, collection, shipment, and storage conditions are the same.

8.11 Unscheduled visit(s)

Unscheduled visits can be performed at any time point when clinically indicated as per the treating provider. These assessments are symptom based and may include additional screening tests and procedures deemed medically necessary by the investigator. The data should be entered in the appropriate unscheduled visit eCRF pages.

8.12 Early termination visit(s)

If, for any reason, patients are permanently discontinued from the trial before completing all scheduled visits, patients will complete an Early Termination Visit. If possible, all assessments planned for the actual week or day of that visit as listed in respective SoA (Section 1.3) and which are not included in the EOT visit should also be performed.

9 STATISTICAL CONSIDERATIONS

Methodology for summary and statistical analyses of the data collected in this trial is described here and further detailed in the statistical analysis plan (SAP), which will be maintained by the sponsor. The SAP may modify what is outlined in the protocol where appropriate; however, any major modifications of the primary endpoint definitions or their analyses will also be reflected in a protocol amendment.

There will be an SRC (for Phase I) and an IDMC (for Phase II). For relevant procedures relating to SRC and IDMC operation (e.g., charter, composition, and schedule of meetings etc.), see Section 10.1.5.

[figure not shown]
9.1 Statistical hypotheses

For the Phase I part of this trial, no formal hypotheses are tested.

For the Phase II part of this trial, the main primary endpoint (i.e., mDFS) will be assessed between the two randomized groups using the two-sided log-rank test, stratified by the randomization strata, at 5% significance level. Considering proportional hazards, i.e., $\lambda_{T(t)} = \theta \ \lambda_{C(t)}$, where λ (t) denotes the hazard at time t in combination group (T) and mFOLFIRINOX group I, respectively, and θ the unknown constant of proportionality of hazards, the following null and alternative hypothesis will be tested:

H0: $\theta = 1$ versus H1: $\theta \neq 1$.

Page 85 of 127 Version: 2.0 Date: 22 JAN 2024

Page 86 of 127 Version: 2.0 Date: 22 JAN 2024

9.3 Sample size determination

The sample size calculation is based on the primary endpoint of mDFS, ensuring that DFS will be adequately powered. The calculation of the required number of events is based on the following specifications:

- 1:1 randomization
- Hazard ratio (HR) = 0.60
- Significance level of α = 5% (two-sided)
- Power of 1- β = 90%

Based on these specifications CC (Section 9.2) at least 164 aggregate events (i.e. 55% maturity) in both arms will be required to demonstrate efficacy assuming a true effect size of HR = 0.60 with a power of 90% using a two-sided statistical test at 5% significance level.

The calculation of the required number of patients is based on the following assumptions:

- Median DFS time from randomization of 21.6 months in the mFOLFIRINOX group and 36 months in the combination group (assume HR = 0.60)
- Accrual duration: ~24 months for Phase I and Phase II
- Follow-up duration: until DFS event
- Drop-out rate: 10% per year

Based on these assumptions at least 300 patients in both arms combined will be required to observe the required number of DFS events (164) ~34 months after last patient in (LPI) (randomized).

9.4 Analysis sets

The following analyses sets are defined:

Analysis set	Description
Screened Set	All patients who gave informed consent
Enrolled Set	All patients who are enrolled into the trial
Full Analysis Set (FAS)	All patients who are randomized into the trial
Modified Full Analysis Set (mFAS)	All patients who received IMP and have a baseline and at least one on- treatment / post-treatment tumor response assessment and satisfy major eligibility criteria
Safety Analysis Set (SAF)	All patients who received IMP (i.e., at least one dose of IMP)
DLT Evaluation Set	All patients who are enrolled in the dose escalation part of the trial (Phase I) and who meet at least one of the following criteria: • Experiences a DLT following at least one dose of BNT321

Page 87 of 127 Version: 2.0 Date: 22 JAN 2024

Analysis set	Description
	Does not experience a DLT, has received at least 80% of the planned BNT321 dose, and is followed for the full DLT assessment period
Per Protocol Set (PP)	All patients who are randomized into the trial and absent of important protocol deviations (as identified throughout the conduct of the trial and before each data cut-off) which are considered to impact the analyses
PD Set	All patients with baseline and at least one valid on-treatment follow-up PD assessment
PK Set	All patients with baseline and at least one valid on-treatment follow-up PK assessment

Abbreviations: DLT = dose-limiting toxicity; IMP = investigational medicinal product; PD = pharmacodynamic; PK = pharmacokinetic.

All safety analyses will be based on the treatment actually taken by the patient ('as treated'). All other analyses will be based on the treatment the patient was assigned / randomized to ('as randomized'), unless stated otherwise.

9.5 Statistical analyses

Statistical analyses will be performed by BioNTech or a designated CRO. All statistical analyses will be carried out using SAS®, Version 9.4 or higher, and/or other statistical software as required.

The SAP will be finalized prior to first database lock for the primary analysis, and it will include a more technical and detailed description of the statistical analyses described in this section. Any deviations from the planned analyses described in the final SAP will be described and justified in the clinical trial report. This section is a summary of the planned statistical analyses of the most important endpoints including primary and key secondary endpoints.

9.5.1 General considerations

In general, the statistical analyses will be performed for Phase I and Phase II parts separately. The Phase I part analysis will be performed by dose level cohort. The Phase II part will be performed by treatment group (i.e., mFOLFIRINOX + BNT321 and mFOLFIRINOX).

Continuous variables will be summarized by treatment group/cohort using the following descriptive statistics: number of patients (n), mean, standard deviation, median, minimum and maximum

Categorical variables will be summarized by treatment group/cohort presenting absolute and relative frequencies (n and %) of patients in each category.

Time-to-event-endpoints will be analyzed using Kaplan-Meier methodology by treatment group/cohort and censored in accordance with the FDA Guidance: "Clinical Trial Endpoints for the Approval of Cancer Drugs and Biologics" and the EMA guidance "Guideline on the

Page 88 of 127 Version: 2.0 Date: 22 JAN 2024

evaluation of anticancer medicinal products in man". Censoring rules will be defined in the SAP.

The median survival time (including two-sided 95% confidence limits according to Brookmeyer and Crowley) and the first and third quartile will be presented for each treatment group/cohort. Survival rates and DFS rates (including two-sided 95% confidence interval based on the Greenwood 1926 formula) as well as the number and percentage of patients with events, censored and under risk will be displayed for selected time points (e.g., at 12, 24, 36 and 48 months).

The survival distributions for two treatment groups will be compared using the stratified log-rank test (stratified by the stratification factors surgical resection status and nodal status at time of resection), and the p-value will be provided. The associated HR and two-sided 95% confidence interval will be estimated by using stratified (i.e., R0 versus R1; pN0 versus pN1) Cox proportional hazard model with treatment as model covariate.

The time-to-event analysis will be illustrated using Kaplan-Meier plots by treatment group and additionally strata. Baseline is defined as last available value prior to randomization (Phase II)/first dose of IMP (Phase I).

Data up to and including the clinical cut-off date for the statistical analysis will be included in the statistical analysis. Handling of missing data will be described in the SAP.

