- 20. Blood chemistry to include sodium, potassium, chloride, bicarbonate, blood urea nitrogen, creatinine, glucose, calcium, phosphate, magnesium, AST, ALT, total bilirubin, alkaline phosphatase, total protein, albumin, and uric acid to be performed at screening, Day 1 of every cycle, Week 25/EOT, at safety FU visit, and as needed according to investigator's discretion based on new symptoms and/or medical concerns.
- 21. Serum amylase, lipase and haptoglobin will be performed on Day 1 of every cycle, Week 25/EOT, and as needed according to investigator's discretion based on new symptoms and/or medical concerns.

Page 24 of 127 Version: 2.0 Date: 22 JAN 2024

- 22. GGT will be performed at screening and on Day 1 of every cycle, Week 25/EOT, and as needed according to investigator's discretion based on new symptoms and/or medical concerns.
- 23. To include color, appearance, glucose, bilirubin, ketone, specific gravity, blood, pH, protein, urobilinogen, nitrite, leukocyte esterase. If warranted by dipstick analysis, microscopic analysis to include RBC, WBC, casts, crystals, epithelial cells, and bacteria. Will be performed at screening, and when clinically indicated.
- 24. For POCBPs only.
- 25. CA19-9 will be measured from blood collected at screening (post-operative measurement required within 3 weeks of C1D1), C1D1, at EOT and at disease assessment timepoints detailed in Footnote 23.
- 26. Disease assessment will consist of imaging by CT/MRI scan and serum CA19-9 and will be performed at screening (baseline post-operative imaging within 4 weeks of C1D1 and serum CA19-9 within 3 weeks of C1D1 are required), and then after C1D1 every 3 months (12 weeks) for 2 years, and then every 6 months for 3 years (±7 days). CT with contrast or MRI (as appropriate for patient, or multiparametric MRI following an inconclusive CT). Patients should be evaluated with the same imaging method (CT or MRI) throughout the trial.
- 27. ADCC, CDC and cytokines will be measured from blood collected prior to dosing of mFOLFIRINOX. Collected on the following days: C1D1, C2D3, C2D8, C4D3, and C4D8. Whole blood collected for PBMC isolation for ADCC assessment will only be collected if logistically manageable.
- 28. FFPE tumor tissue from surgical resection is required during screening. In the event of progression, if a biopsy is performed, a sample (optional) should be requested.

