Serum CA19-9 levels have been found to be informative with respect to prognosis and treatment effect in patients with pancreatic cancer, with several studies correlating increasingly higher serum levels with poorer survival outcomes (Ballehaninna et al. 2012; Dong et al. 2014; Berger et al. 2004). In a Phase I/II clinical trial in advanced pancreatic cancer, decreases in CA19-9 levels correlated with tumor response, PFS, and OS (von Hoff et al. 2011). In a Phase II trial of 5-flurouracil-based chemo-radiotherapy in patients with locally advanced pancreatic cancer, a greater than 90% reduction in CA19-9 levels from baseline was associated with significantly improved median survival times, and in a multivariate analysis, a post therapy CA19-9 level of less than 85.5 U/mL was found to be an independent prognostic factor for survival (Yang et al. 2013). Because CA19-9 is highly expressed in pancreatic cancer, it was identified as a target for antibody-based biopharmaceuticals.

BNT321 (previously known as MVT-5873) is a fully human IgG1 lambda antibody discovered by MabVax in collaboration with investigators at Memorial Sloan Kettering Cancer Center (MSKCC). BNT321 was identified from blood lymphocytes following immunization with a sLe^a-KLH vaccine for the treatment of breast cancer (Ragupathi et al. 2009). This vaccine has been shown to induce high titers of both immunoglobulin G (IgG) and IgM antibodies against sLe^a in mice and humans without cross-reactivity to other similar blood group carbohydrate antigens (Ragupathi et al. 2009).

BNT321 binds specifically to the cancer associated sLe^a carbohydrate epitope and does not bind to Le^a, sLe^x, Le^y, or other related carbohydrates when evaluated by enzyme-

Page 35 of 127 Version: 2.0 Date: 22 JAN 2024

linked immunosorbent assay (ELISA) and surface plasmon resonance. In addition, an independent binding analysis on a glycan array with 465 distinct carbohydrates revealed that BNT321 had exquisite specificity for the carbohydrate epitope of the sLe^a antigen. Evaluation for specificity in tumors revealed BNT321 demonstrated cell surface binding in multiple CA19-9 expressing malignancies including pancreatic cancer cell lines (BxPC3 and Capan 2, both sLe^a positive), but not in CA19-9 negative melanoma cell line SKMEL28 (sLe^a negative) (BNT321 investigator's brochure [IB]).

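### Baseline CA19-9 is mandatory in both arms and described as prognostic, but the stratified Cox model does not adjust for it: a forgone gain in precision, not an error

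*Combined protocol and SAP*

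**What the plan says.** - **Primary test.** Section 9.1 compares DFS between arms with a two-sided log-rank test at 5%, stratified by the randomization strata.
- **HR.** Section 9.5.1 takes the HR and its 95% interval from a "Cox proportional hazard model with treatment as model covariate". The words just before that quote stratify the model by R0/R1 and pN0/pN1. These are the randomization strata of Section 6.6.2, and Section 4.2.2 justifies them as important for outcome.
- **CA19-9 as a prognostic marker.** Section 2.2.2 states: "Serum CA19-9 levels have been found to be informative with respect to prognosis and treatment effect in patients with pancreatic cancer". It adds that several studies link higher levels to poorer survival, but it gives no hazard ratio.
- **Availability.** Section 1.3 requires the value in both arms (Table 2 footnote 26, Table 4 footnote 25): "CA19-9 will be measured from blood collected at screening (post-operative measurement required within 3 weeks of C1D1), C1D1". Exclusion criterion 16 in Section 5.3 removes patients above 180 U/mL.
- **Planned use.** Section 3 lists the relation of CA19-9 to clinical outcome as an exploratory objective. CA19-9 is neither a randomization stratum nor a covariate.

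**The concern.** The reasoning that justifies R0/R1 and pN0/pN1 applies equally to CA19-9, and the value will be available for nearly every patient because eligibility depends on it. Leaving a prognostic covariate out of a Cox model has two consequences. The treatment-only HR lies nearer 1 than the HR conditional on the covariate, and a test using the covariate would have somewhat more power at the same number of events. In addition, a chance difference in CA19-9 between arms carries into the estimated HR. CA19-9 is also the target of BNT321, so readers are likely to check this marker early. An adjusted analysis chosen after such an imbalance is seen would carry less weight than a prespecified one.

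**Working it through.** **1. The plan's own figure.** Inputs from Section 9.3: "1:1 randomization", "Hazard ratio (HR) = 0.60", two-sided alpha 5%, power 90%.

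Schoenfeld events = 4(1.960 + 1.282)² / (ln 0.60)² = 161.07, so 162 against the stated 164. The small difference may come from Section 9.2, which is redacted. Power at 164 events: (√164 / 2) × 0.5108 − 1.960 = 1.311, which gives 90.5%. The plan's figure is reproduced.

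**2. Which HR is 0.60?** Section 9.3 assumes "Median DFS time from randomization of 21.6 months in the mFOLFIRINOX group and 36 months in the combination group". 21.6/36 = 0.60 is a ratio of arm-level medians and is not conditional on CA19-9. The 90.5% therefore already describes an analysis without CA19-9.

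**3. Simulation.** 300 patients, analysis at 164 events, control median 21.6 months, 24-month uniform accrual, drop-out 10% per year, Cox model stratified by R0/R1 × pN0/pN1, with and without a standardized CA19-9 term. Power is the Wald test in favour of the combination. The stratified log-rank is the score test of the treatment-only model, so its power should be very close. Assumptions not in the documents: R1 40%, pN1 75%, log-HR 0.35 for each stratum factor, a normally distributed CA19-9 term, and the CA19-9 effect itself.

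*Reading A: 0.60 is the HR conditional on CA19-9 (2,500 runs).*

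| log-HR per SD | HR per SD | treatment-only HR | power without | power with | difference |
|---|---|---|---|---|---|
| 0 | 1.00 | 0.604 | 89.3% | 89.0% | −0.3 |
| 0.2 | 1.22 | 0.607 | 87.6% | 88.8% | 1.2 |
| 0.3 | 1.35 | 0.611 | 86.0% | 88.8% | 2.8 |
| 0.4 | 1.49 | 0.617 | 86.1% | 89.7% | 3.6 |
| 0.5 | 1.65 | 0.630 | 83.1% | 89.3% | 6.2 |
| 0.7 | 2.01 | 0.650 | 76.2% | 89.0% | 12.8 |

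*Reading B: the treatment-only HR is about 0.60, as the medians imply (1,500 runs).*

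| log-HR per SD | conditional HR | treatment-only HR | power without | power with | difference |
|---|---|---|---|---|---|
| 0.3 | 0.585 | 0.594 | 90.4% | 91.7% | 1.3 |
| 0.5 | 0.565 | 0.591 | 91.4% | 93.8% | 2.4 |
| 0.7 | 0.540 | 0.594 | 90.3% | 96.8% | 6.5 |

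Simulation error is about 0.5 to 1 point per power figure.

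**4. Rough ceiling under Reading B.** At log-HR 0.5, Reading A shrinks the log-HR by ln 0.630 / ln 0.60 = 0.904. A treatment-only HR of 0.60 then corresponds to a conditional log-HR of 0.5108 / 0.904 = 0.565. Power at 164 events: 6.403 × 0.565 − 1.960 = 1.66, or 95.1%, which is 4.6 points above 90.5%. This ignores the slightly larger standard error after adjustment, so it overstates the gain. Together with the simulated 1.3 and 2.4, about 1 to 4 points is a fair range for log-HR 0.3 to 0.5.

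**5. Validity.** Under the null (log-HR 0.5 per SD, 1,500 runs) the treatment-only analysis rejected in favour of the combination in 2.0% of runs, against a nominal 2.5%. There is no inflation.

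**6. Chance imbalance.** With 150 per arm, the difference in mean CA19-9 has standard deviation √(2/150) = 0.115 SD. A difference of 1.96 × 0.115 = 0.226 SD or more, in either direction, has about a 5% chance. At log-HR 0.3 to 0.5 this multiplies the HR by roughly exp(0.068) = 1.07 to exp(0.113) = 1.12. An HR of 0.60 would then read about 0.64 to 0.67, or 0.56 to 0.54 the other way.

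**The case against.** A reader might infer that the model adjusts for nothing, that the HR is biased toward 1, and that the trial has about 85% power or less instead of 90%. The documents support none of these.

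- The model is already stratified by two factors that the protocol regards as important for outcome.
- The shift in the HR is non-collapsibility. The treatment-only HR is a valid, different estimand, and it is the one on which the sample size rests.
- Power below 90% appears only under Reading A, whereas Section 9.3 derives 0.60 from unadjusted medians.
- The p-value comes from the stratified log-rank. Adding CA19-9 to the Cox model alone does not change the power of that test.

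These objections stand, and they limit the point to efficiency.

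Three further objections carry part of their weight. First, prognostic strength in this population is undocumented. The two trials that Section 2.2.2 describes in detail concern advanced or locally advanced disease, and the 180 U/mL cap narrows the spread. That makes the size of the gain uncertain, but two of the papers cited there have titles naming resectable disease, so the marker is not irrelevant here. Second, CA19-9 is the drug target, so a main-effect term may not capture everything. An adjusted HR shown beside the unadjusted one does not require that it should. Third, Section 9.5 calls itself a summary and leaves detail to a later SAP, which could still add the covariate. That is a reason to raise the point now.

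Chance imbalance is no threat to validity either: the confidence interval allows for it on average over randomizations. Adjustment helps in reading the particular allocation obtained.

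**Conclusion.** The point holds as a suggestion for efficiency and robustness. The planned analysis is valid, consistent with its sample-size basis, and has about 90% power at HR 0.60 with 164 events. Leaving out CA19-9 forgoes about 1 to 4 power points for an assumed log-HR of 0.3 to 0.5 per SD, and only if the adjusted test were the one used. With the log-rank as test of record, the benefit is an HR estimate less exposed to a chance difference in CA19-9.

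The size rests on an effect that the documents do not give. It would be smaller if the entry cap weakens the effect per SD, and larger if CA19-9 is more strongly prognostic within the eligible range (about 6 points at 0.7 per SD under Reading B). The required 164 events do not change.

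**What to change.** Before any unblinded comparison, prespecify in the SAP log-transformed CA19-9 as a covariate in the Cox model stratified by R0/R1 and pN0/pN1, for DFS, OS and RFS, and report that HR beside the treatment-only HR. Waiting for database lock, as Section 9.5 allows, is too late for this purpose: site staff know the allocation (Section 6.6.3) and the IDMC reviews unblinded primary endpoint data (Section 10.1.5).

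Name the value used. Section 9.5.1 defines the Phase II baseline as the last value before randomization. Randomization may take place between Day −3 and C1D1, so the C1D1 sample can fall after it, and the screening sample will normally be the one. State also how undetectable and missing values are handled.

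Keeping the stratified log-rank as the test of record costs SAP wording only and needs no new data. Making the adjusted Cox test the test of record would bring the power gain, but it changes the primary analysis and so needs a protocol amendment under Section 9. The small downside of either option is that the adjusted HR is conditional on CA19-9, so both HRs must be shown.
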